4.3.1 PT2385 Administration

PT2385 will be administered on an outpatient basis as an oral dose of 800 mg twice daily. Patients should take the doses approximately the same time each day. Each dose should be taken 12 hours apart (\pm 2 hours). Tablets should be taken with 8 ounces of water and

may be taken with or without food. Tablets should be swallowed whole, not chewed or crushed.

Missed doses may be made up if taken within 4 hours after the scheduled administration time. Study drug may not be taken within 8 hours before the scheduled time for administration of the next dose. Patients who vomit after study drug administration should not retake that study drug dose but should resume taking study drug with the next scheduled dose.

Patients will be requested to record each dose of PT2385 on the Patient Medication Diary in [Appendix I](#).

4.4 General Concomitant Medication and Supportive Care Guidelines

Prohibited Concomitant Medications During Study

Patients may receive other medications that the investigator deems to be medically necessary, with the specific exception of non-protocol specified chemotherapy, radiotherapy, anti-neoplastic biological therapy or other investigational agents. Patients who require the use of any of the aforementioned treatments for clinical management should be removed from the study.

PT2385 is primarily metabolized by UGT2B17, UGT2B7, UGT2B15, CYP2C19 and CYP3A4. Strong inhibitors of CYP2C19 and CYP3A4 should be avoided in patients receiving PT2385 ([Appendix II](#)).

PT2385 has been shown to induce the enzymes CYP3A4 and CYP2B6 in cultured human hepatocytes. Simcyp PBPK model simulations indicate weak-to-moderate CYP3A4 substrate midazolam DDIs (~50% reduction in midazolam AUC) at the clinically relevant PT2385 doses. Simulations also indicate that PT2385 is a weak CYP2B6 inducer (< 11% AUC reduction for CYP2B6 substrate bupropion at the clinically relevant PT2385 doses). PT2385 is not a potent inhibitor for CYP1A2, CYP2B6, CYP2C8, CYP2C9, CYP2C19, CYP2D6 and CYP3A4 ($IC_{50} > 8.8 \mu\text{g/mL}$). It is unlikely to significantly inhibit these CYPs at the clinically relevant PT2385 concentrations ($C_{\text{max}} \sim 3.14 \mu\text{g/mL}$). A partial list of CYP3A4, CYP2B6, CYP2C9, and CYP2C19 substrates is provided in [Appendix III](#).

Patients taking medications metabolized by CYP3A4 and CYP2B6 should be monitored carefully for decreases in drug effect. Patients taking medications metabolized by CYP2C9 and CYP2C19 should be monitored for potential increases in drug effect.

Corticosteroids

Postoperatively, corticosteroids should be tapered to a stable dose as determined by the clinical status of the patient. The lowest required steroid dose should be maintained throughout the duration of the study in order to eliminate steroid effects as a confounding variable in the interpretation of serial brain imaging studies. Corticosteroid doses can be tapered as clinically indicated if the patient appears to be responding to therapy as judged by serial scans. Corticosteroid dose may, of course, be increased in the event of clinical deterioration or at the discretion of the attending physician. In the event of suspected clinical deterioration, repeat brain imaging is recommended.

Anticonvulsants

No data exist regarding the interaction of PT2385 with enzyme-inducing anti-epileptic drugs (EIAEDs). For this study, patients may **not** be on EIAEDs; patients who require antiepileptic drugs (AED) may be on non-enzyme inducing anti-epileptic drugs (NEIAED). If a patient on this study protocol needs to have an AED started or needs to have a second AED added then only NEIAED should be used. There must be a ≥ 10 day period from discontinuation of an EIAED and initiation of therapy. In the event that an EIAED drug must be used for a patient on study the patient will be removed from the protocol.

Herbal and Non-Traditional Medications

No data exist regarding the interaction of PT2385 with commonly used herbal or nontraditional medications. Patients should be instructed not to use such medications while receiving PT2385 therapy.

5.0 DOSING DELAYS/DOSE MODIFICATION FOR TOXICITY

Clinically significant adverse events or abnormal laboratory values assessed as unrelated to disease progression, intercurrent illness, or concomitant medications may require dose delay and/or dose modification. Such toxicities must have an attribution of possible, probable, or definite to PT2385 (see Section [9.2.2](#)). If multiple toxicities occur, dose modification decisions should be based on the most severe toxicity.

For patients experiencing toxicity meeting the criteria below, PT2385 will be stopped. If the patient recovers (\leq grade 1 [or tolerable grade 2 for non-hematologic toxicity] or \leq baseline) a dose reduction is required for subsequent doses. Skipped doses will not be made up. If there is any question or clarification required concerning a toxicity, the treating site should contact the ABTC Central Office to determine patient's toxicity status. The ABTC Central Office, with the Study Chair (who may consult with Peloton Medical), will make the final decision.

- Hematological toxicities will require dose modification if any of the following occur and complete blood counts and differentials were obtained according to the

mandated schedule (CBC, differential, and platelets drawn twice a week until the ANC \geq 1500/ mcL and platelets \geq 100,000/ mcL): grade 3 or 4 lymphopenia will not be considered a toxicity requiring dose modification.

- ANC of $<$ 500/ mcL
- Platelets $<$ 25,000/ mcL
- Febrile neutropenia
- Any hematological toxicity that prevents administration of \geq 80% of the planned PT2385 doses for that cycle

➤ Non-hematological toxicities will require dose modification if any of the following occur:

- Grades 3-4 severity (except nausea, vomiting, and diarrhea without sufficient prophylaxis; except alopecia; except grade 3 hyperglycemia; except grade 3 electrolyte disturbances that are asymptomatic and that respond to replacement therapy; and except grade 3 neurologic toxicity responding within two weeks to steroids, anticonvulsants, or electrolyte correction; and except Grade 3 asymptomatic hypoxia. A subject's first episode of deep venous thrombosis [DVT] or pulmonary embolism [PE] will not require dose modification)

ANY TREATMENT RELATED TOXICITY (AS DEFINED ABOVE) CAUSING DELAY IN TREATMENT OF OVER 21 DAYS IN THE START OF A CYCLE WOULD RESULT IN TAKING THE PATIENT OFF TREATMENT.

5.1 Dose Modification for PT2385

The dose levels and the general approach to PT2385 dose modification on this trial are shown below. Adverse events (AEs) should be treated with the appropriate maximum supportive care, and dose reductions should be clearly recorded on the case report form.

Dose reductions are required for any clinically significant toxicity as defined above. Dosing will stop until the toxicity has resolved to \leq grade 1 (or tolerable grade 2 for nonhematologic toxicity) or \leq baseline. After resolution, when dose reduction is permitted, the dose of PT2385 will be modified as stipulated below, with a maximum of 2 dose reductions. The maximum length of time that PT2385 can be held is 21 days. If treatment-related toxicity is not resolved in \leq 21 days, the patient will be removed from treatment. If there is any question, the ABTC Central Office and the Study Chair should be contacted. The ABTC Study Chair may consult with Peloton Medical as needed for any issues.

Dose Reduction Table for PT2385

Dose Level	PT2385
Starting dose	800 mg b.i.d.
First dose reduction	600 mg b.i.d.
Second dose reduction	400 mg b.i.d.

5.2 Major Events

Major Events are non-treatment-related grade 3 and 4 hematologic and non-hematologic toxicities. Treatment should be delayed for major events if PT2385 may further complicate the non-treatment-related event. If a major event requires a delay of treatment, treatment must be delayed until toxicity is resolved (\leq grade 1 [or tolerable grade 2 for nonhematologic toxicity] or \leq baseline). If toxicity is not resolved in \square 28 days, the patient will be removed from treatment. The ABTC Central Office should be consulted if you are not clear on whether to continue or delay treatment.

5.3 Use of Hematologic Growth Factors

During the first 28 days of treatment, granulocyte colony stimulating factor (G-CSF) should be administered only for severe or prolonged neutropenia or for neutropenic sepsis. There will be no constraint on the use of growth factors during subsequent treatment; however, prophylactic use is discouraged and adherence to the American Society of Clinical Oncology (ASCO) guidelines is recommended (JCO, 12, 1994: pp 2471-2508). Patients should receive all necessary supportive care, including blood products, transfusions, antibiotics, pain medications, bisphosphonates, and replacement hormonal therapies (insulin, thyroid hormones, estrogen/progesterone).

5.4 Toxicity Criteria

All toxicities will be described and graded according to the NCI Common Terminology Criteria for Adverse Events (CTCAE) version 4.0 until March 31, 2018; CTCAE version 5.0 will be utilized beginning April 1, 2018. All appropriate treatment areas should have access to a copy of the CTCAE version 5.0. A copy of the CTCAE version 5.0 can be downloaded from the CTEP web site (http://ctep.cancer.gov/protocolDevelopment/electronic_applications/ctc.htm). See also Section [9.2.2](#), Recording of Adverse Events.

[figure not shown]
6.0 PHARMACEUTICAL INFORMATION

PT2385

Chemical Name: 3-(((1*S*)-2,2-difluoro-1-hydroxy-7-methanesulfonyl-2,3-dihydro-1*H*inden-4-yl)oxy)-5-fluorobenzonitrile

Other Names: PT2385, PT-2385, PT0002385 and CK 1558

Chemical Structure:

Molecular Formula: C₁₇H₁₂F₃NO₄S. **M.W.:** 383.34 g/mol

Chemical Properties: PT2385 has low solubility in water. The Log D value for PT2385 in octanol/water pH 7.4 is 2.19.

Pharmaceutical Properties: PT2385 is an anticancer agent that inhibits the function of HIF-2 α by disrupting the formation of the HIF-2 α :ARNT heterodimer with consequent impairment of hypoxic signaling in cancer cells.

Formulations: PT2385 is formulated as an immediate release tablet in a 200 mg strength. The excipients used in the formulation include United States Pharmacopeia or National Formulary grade lactose monohydrate, microcrystalline cellulose, croscarmellose sodium, hydroxypropyl cellulose, polysorbate 80 and magnesium stearate.

Storage: PT2385 tablets are to be stored at room-temperature conditions, 15°C to 30°C (59°F to 86°F).

Stability: Studies are ongoing to monitor the stability of PT2385 tablets.

Route of Administration: Oral, given with or without food. Each dose should be taken with 8 ounces (240 mL) of water.

6.1 Agent Ordering

The investigator or those named as sub-investigators on the Statement of Investigator Form 1572 agree to supply study drugs only to those patients enrolled in the study. The

investigator or designee will keep a current and accurate inventory of all clinical drug supplies provided by Peloton Therapeutics. The study site will maintain a dispensing log.

Once a site has submitted all required regulatory documents to ABTC and Peloton (Forms 1572, CVs, licenses, IRB protocol approval) an initial supply of drug can be ordered. An ABTC drug order form, which can be found on the ABTC website (ABTCConsortium.org), should be emailed to the ABTC Central Office to initiate sending drug. The ABTC Central Office will forward the drug order form to Peloton. Please allow a minimum of 7 days from the receipt of the drug order at Peloton for drug shipment.

6.2 Agent Accountability

Each institutional investigator, or a responsible party designated by the investigator, must maintain a careful record of the inventory and disposition of all drugs received from Peloton, using the NCI Oral Drug Accountability Record Form (Oral DARF).

Upon termination of the study the investigator or designee must complete a final inventory of supplies.

7.0 PROCEDURES FOR PATIENT ENTRY ON STUDY

This study is supported by the NCI Cancer Trials Support Unit (CTSU) Regulatory Office and uses the Oncology Patient Enrollment Network (OPEN).

CTEP Registration Procedures

Food and Drug Administration (FDA) regulations and National Cancer Institute (NCI) and ABTC policy require all investigators participating in any NCI-sponsored clinical trial to register and to renew their registration annually.

Registration requires the submission of:

- a completed **Statement of Investigator Form** (FDA Form 1572) with an original signature
- a current Curriculum Vitae (CV)
- a completed and signed **Supplemental Investigator Data Form** (IDF)
- a completed **Financial Disclosure Form** (FDF) with an original signature

Fillable PDF forms and additional information can be found on the CTEP website at http://ctep.cancer.gov/investigatorResources/investigator_registration.htm.

For questions about Investigator Registration, please contact the **CTEP Investigator Registration Help Desk** by email at [contact].

Site Registration Requirements – IRB Approval

Each investigator or group of investigators at a clinical site must obtain IRB approval for this protocol and submit IRB approval and supporting documentation to the CTSU Regulatory Office before they can enroll patients. Study centers can check the status of their registration packets by querying the Regulatory Support System (RSS) site registration status page of the CTSU member web site by entering credentials at <https://www.ctsu.org> and clicking on the RSS tab.

Site registration documents must be submitted to the Regulatory Submission Portal of the CTSU Member Web site (login is required). To access the Regulatory Submission Portal, the site staff must have an Active CTEP IAM account. Site staff can utilize the Regulatory Submission Portal at any time by clicking the “Regulatory submission” subtab under the “Regulatory” Tab, located at the top of all pages on the CTSU members’ website. (See Regulatory Submission Portal User Guide 12.6.16 on CTSU website (www.ctsu.org) for detailed instructions on how to use portal).

Patient Registration:

Patient enrollment will be facilitated using the Oncology Patient Enrollment Network (OPEN). All site staff will use OPEN. OPEN is a web-based registration system available to users 9 a.m. to 4:30 p.m. Eastern Time. The system can be accessed by entering credentials at <https://www.ctsu.org> and clicking on the OPEN tab, or by entering credentials at the OPEN portal URL <https://open.ctsu.org>.

Prior to discussing protocol entry with the patient, site staff must check the ABTC website (ABTConsortium.org) for protocol status and slot availability.

Prior to accessing OPEN, site staff should verify the following:

- All eligibility criteria have been met within the protocol stated timeframes. Site staff should use the registration forms provided on the group web site as a tool to verify eligibility.
- All patients have signed an appropriate consent form and HIPAA authorization form (if applicable).

Access requirements for OPEN:

- Site staff will need to be registered with CTEP and have a valid and active CTEP-IAM account. This is the same account (user id and password) used for credentialing in the CTSU members' web site.
- To perform registrations, the site user must have been assigned the 'Registrar' role (or equivalent) on the relevant Group or CTSU roster.

The OPEN system will provide the site with a printable confirmation of registration and treatment information. Upon completion of the registration process in OPEN, sites should contact the ABTC Central Office to confirm the patient's registration.

Further instructional information is provided on the CTSU members' web site OPEN tab or within the OPEN URL (<https://open.ctsu.org>). For any additional questions contact the CTSU Help Desk at [name] or [contact].

8.0 RESPONSE ASSESSMENT / SAFETY AND QUALITY ASSURANCE

8.1 Criteria for Response Assessment

Subjects with measurable disease will be assessed by the RANO (radiographic assessment in neuro-oncology) criteria (Wen et al., 2010). For the purposes of this study, subjects should be re-evaluated at the end of every 2 cycles (approximately every 8 weeks) with a contrast-enhanced cranial MRI scan. The response will be determined as outlined in the RANO criteria below.

Measurable disease. Bidimensionally, contrast-enhancing, measurable lesions with clearly defined margins by MRI scan, with a minimal size of 1 cm x 1 cm, and visible on 2 axial slices which are at least 5 mm apart with 0 mm skip. Measurement of tumor around a cyst or surgical cavity, if necessary, requires a minimum thickness of 3 mm. If there are >2 lesions (multifocal) at baseline, the investigator must choose the largest two to be followed before a participant is entered on study. The remaining lesions will be considered nonmeasurable for the purpose of objective response determination. Unless progression is observed, objective response can only be determined when all measurable and nonmeasurable lesions are assessed.

Complete Response – CR (requires *all* of the following):

- a) Complete disappearance of all enhancing measurable and non-measurable disease sustained for at least 4 weeks. In the absence of a confirming scan 4 weeks later, this scan will be considered only stable disease.
- b) No new lesions.
- c) All measurable and non-measurable lesions must be assessed using the same techniques as baseline.
- d) Subjects must be off corticosteroids (or on physiologic replacement doses only).
- e) Stable or improved non-enhancing (T2/FLAIR) lesions.
- f) Stable or improved clinically.

Note: Subjects with non-measurable disease cannot have a complete response. The best response possible is stable disease.

Partial Response – PR (requires *all* of the following):

- a) Greater than or equal to 50% decrease compared to baseline in the sum of products of perpendicular diameters of all measurable enhancing lesions sustained for at least 4 weeks. In the absence of a confirming scan 4 weeks later, this scan will be considered only stable disease.
- b) No progression of non-measurable disease.
- c) No new lesions.
- d) All measurable and non-measurable lesions must be assessed using the same techniques as baseline.
- e) The corticosteroid dose at the time of the scan evaluation should be no greater than the dose at time of baseline scan.
- f) Stable or improved non-enhancing (T2/FLAIR) lesions on same or lower dose of corticosteroids compared to baseline scan. g) Stable or improved clinically.

Note: Subjects with non-measurable disease cannot have a partial response. The best response possible is stable disease.

Stable Disease – SD (requires *all* of the following):

- a) Does not qualify for CR, PR, or progressive disease (PD).
- b) The designation of stable disease requires a minimum of 4-week duration.
- c) All measurable and non-measurable sites must be assessed using the same techniques as baseline.
- d) Stable non-enhancing (T2/FLAIR) lesions on same or lower dose of corticosteroids compared to baseline scan. In the event that the corticosteroid dose was increased for new symptoms and signs without confirmation of disease progression on neuroimaging, and subsequent follow-up imaging shows that this increase in corticosteroids was required because of disease progression, the last scan considered to show stable disease will be the scan obtained when the corticosteroid dose was equivalent to the baseline dose. e) Stable clinically.

Progressive Disease – PD (defined by *any* of the following):

- a) $\geq 25\%$ increase in sum of the products of perpendicular diameters of enhancing lesions compared to the smallest tumor measurement obtained either at baseline (if no decrease) or best response, on stable or increasing doses of corticosteroids.*
- b) Significant increase in T2/FLAIR non-enhancing lesion on stable or increasing doses of corticosteroids compared to baseline scan or best response following initiation of therapy,* not due to co-morbid events (radiation therapy, demyelination, ischemic injury, infection, seizures, postoperative changes, or other treatment effects). c) Any new lesion.
- d) Clear clinical deterioration not attributable to other causes apart from the tumor (e.g., seizures, medication adverse effects, complications of therapy,

cerebrovascular events, infection, etc.) or changes in corticosteroid dose. The definition of clinical deterioration is left to the discretion of the treating physician, but it is recommended that a decrease in 20% of KPS or from any baseline to 50% or less be considered, unless attributable to comorbid events.

- e) Failure to return for evaluation due to death or deteriorating condition.
- f) Clear progression of non-measurable disease.

* Stable doses of corticosteroids include patients not on corticosteroids.

8.2 Assessment of Response

Assessment of response will begin with the MRI performed just prior to *every oddnumbered* treatment cycle. If during any scheduled MRI, the subject has a Complete Response or Partial Response, the MRI should be repeated prior to the next cycle. All scans are to be compared to the smallest measurement scan to date. The subject will then return to the every odd-numbered cycle schedule. This is required to confirm the duration of response. Subjects will be classified as responders if they have a minimum duration of response for 4 weeks at any time after the first cycle of PT2385. MRI scans of subjects showing tumor response will be centrally reviewed by a neuroradiologist who will independently assess tumor size and compute percent tumor regression.

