4.1 Treatment Schema

The goal of this study is to estimate the efficacy of PT2385 as measured by radiographic response in recurrent GBM.

Following enrollment, patients will receive PT2385 at the recommended phase II dose of 800 mg twice daily, continuously in 28-day cycles until progression or unacceptable toxicity. Patients will be followed by routine blood work, and general and neurological examination. A brain MRI will be performed prior to every odd-numbered cycle (every 8 weeks). Response will be assessed by RANO criteria (Section [8.1](#)).

Blood samples to characterize the plasma pharmacokinetics and pharmacodynamics of PT2385 will be obtained from all patients at baseline and in Weeks 1, 2, and 4 of the first

cycle (see Sections [9.5.1](#) and [9.5.2](#)). A blood sample for pharmacogenomic assessment will also be obtained at baseline (Section [9.5.3](#)).

Patients at qualified sites will have simultaneous pH- and hypoxia-weighted MRI performed at baseline (Section [9.5.4](#)).

Patients will continue receiving PT2385 until they meet the criteria for disease progression or other criteria for going off treatment (Section [10.0](#)). Standard of care treatment options will exist for patients who suffer tumor progression or recurrence on treatment. All patients will be followed for progression-free and overall survival. Overall survival will be assessed as the date from treatment start to death from any cause.

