9.5.4 Exploratory pH and Hypoxia MRI (All Patients at Select Sites)

The following correlative imaging will be performed at baseline on all patients at sites with advanced imaging capabilities as defined below.

Simultaneous pH- and hypoxia-weighted MRI using multi-echo amine chemical exchange saturation transfer spin-and-gradient echo echo planar imaging (ME-aCEST-SAGE-EPI):

The correlative imaging components of the study are purely exploratory. The purpose is to investigate whether baseline imaging phenotypes derived from pH- and hypoxiaweight imaging predict patients that will respond from inhibition of HIF2a. We hypothesize that patients with acidic or hypoxic tumors will likely express high levels of HIF2a, making these patients particularly amenable to HIF2a inhibitor treatment.

In this study we will perform a single image acquisition to simultaneously quantify pH and hypoxia using a custom multi-echo amine chemical exchange saturation transfer spin-and-gradient echo echo planar imaging (ME-aCEST-SAGE-EPI) technique. We will quantify (1) the magnetization transfer ratio asymmetry at the amine proton off-resonance frequency ($MTR_{asym} @ 3ppm$) as a measure of tumor acidity and (2) R_2' or $rOEF$ estimates ($rOEF = R_2' / (c * rCBV)$) as a measure of tissue hypoxia. These studies will be performed only at baseline, prior to treatment initiation, to explore whether baseline acidity or hypoxia predict patients that will respond to HIF2a inhibition.

Simultaneous pH- and hypoxia-weighted MRI will be performed at baseline only with Siemens 3T MR systems, which are available at 7 of the 11 ABTC sites. Thus, correlative

imaging data will be restricted to those patients enrolled at these sites. Based on prior enrollment data and experience within the ABTC, we anticipate that at least 25 patients (if the study proceeds to full enrollment) or 16 patients (i.e. if early stoppage criteria are met) to be analyzable for this exploratory objective. Of note, this study is not designed to validate these imaging sequences, as all correlative imaging is strictly exploratory and optional. Acidity and hypoxia imaging scans are purely investigational and will NOT be used for efficacy measurements. Efficacy will be determined by radiographic response and PFS using RANO criteria alone.

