10.1 Off Treatment Criteria

1. **Disease Progression:** Remove patient from protocol therapy at the time progressive disease is documented. Disease progression is defined as: Progressive neurologic abnormalities not explained by causes unrelated to tumor progression (e.g. anticonvulsant or corticosteroid toxicity, electrolyte abnormalities, hyperglycemia, etc.) or a greater than 25% increase in the measurement of the tumor by MRI scan. If neurologic status deteriorates, on a stable or increasing dose of steroids, or if new lesions appear on serial MRI, further study treatment will be discontinued.
2. **Adverse Event:**
 - Intercurrent illness that prevents further administration of treatment
 - Patients who experience unacceptable toxicity. Patients removed from study for unacceptable adverse events will be followed until resolution or stabilization of the adverse event.
3. **Patient Withdrawal:** Patient's refusal to continue treatment: in this event, document the reason for withdrawal.

4. **Non-Compliance:** Failure to comply with protocol (as judged by the investigator such as compliance below 80%, failure to maintain appointments, etc.)
5. **Physician Decision:** If at any time the treating physician feels constraints of this protocol are detrimental to the patient's health remove the patient from protocol therapy.
6. **Protocol Defined Delay:**
 - Patients who experience a treatment-related toxicity causing a delay in treatment >21 days
 - Delay in protocol >28 days for major events or other non-treatment related delays
 - Patients who require >2 dose reductions
 - Patients who must be put on an enzyme-inducing anti-epileptic drug (EIAED) during the study
7. **Death**

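### Section 8.2 compares every scan with the smallest scan to date, while Section 8.1 measures partial response from baseline; applied to response, the 8.2 sentence can miss gradual responders on the primary endpoint

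*Combined protocol and SAP*

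**What the plan says.** Section 8.1 gives each category its own size reference. PR (a) requires "Greater than or equal to 50% decrease compared to baseline in the sum of products of perpendicular diameters", held for at least 4 weeks; without a confirming scan the result counts as stable disease. PD (a) requires a rise of at least 25% "compared to the smallest tumor measurement obtained either at baseline (if no decrease) or best response". The smallest measurement is therefore a size reference for progression only.

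Section 8.2 covers the scan schedule and the repeat MRI that follows a complete or partial response. In that paragraph it states: "All scans are to be compared to the smallest measurement scan to date". The sentence does not mention progression, does not refer back to 8.1 and has no exception for response. The same section asks the central neuroradiologist for a percentage regression and names no reference scan.

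Section 8.4 (Neuroradiology) limits central review to patients whose response was first assessed locally. Section 11.0 makes CR plus PR the primary endpoint. The trial stops at 1 or fewer responders in 24, and the null is rejected at 5 responders in 35.

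**The concern.** The two sections give different comparators for the same scan. Once a tumour has shrunk at all, the smallest earlier scan lies below baseline, and a 50% fall from it is a stricter test than a 50% fall from baseline. A patient whose tumour shrinks in steps could meet the PR size criterion in 8.1 and never meet it against the 8.2 comparator.

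Such a miss is hard to recover. Central review does not see a patient whom the site has not flagged. The 4-week repeat MRI is also triggered only when a response is recognised, so the next scheduled scan would be about 8 weeks later. A response lost by then could not be confirmed, even on re-reading. This bears on the primary endpoint of a multicentre trial in which local reads decide who is reviewed.

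**Working it through.** **1. The plan's own design figures (Section 11.0).** Inputs: 24 patients at stage 1, stop at 1 or fewer responders; 11 more patients, reject at 5 or more of 35; response rates 5% (null) and 20%.

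- Early stopping = (1−p)^24 + 24·p·(1−p)^23. At p = 0.05 this is 0.6608; at p = 0.20 it is 0.0331. The plan states 0.661 and 0.033.
- Rejection probability = sum over x = 2 to 24 of P(X1 = x)·P(X2 ≥ 5 − x), with X1 ~ Bin(24, p) and X2 ~ Bin(11, p). At p = 0.05 this is 0.0284; at p = 0.20 it is 0.8517. The plan states a 5% false positive rate and 85% power.

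The design reproduces. No stated figure is in dispute.

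**2. When the two comparators disagree.** Set baseline to 100. Let s be the smallest scan so far, baseline included, and y the new scan.

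- Rule A (8.1): PR size criterion met if y ≤ 50.
- Rule B (8.2 applied to PR): met if y ≤ s/2.

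Since s ≤ 100, Rule B is never easier than Rule A, so it can only remove responders. A first qualifying scan is missed when 50 < s < 100 and s/2 < y ≤ 50:

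- s = 90: y above 45 up to 50 (falls from baseline of 50% to just under 55%)
- s = 70: y above 35 up to 50 (50% to just under 65%)
- s = 60: y above 30 up to 50 (50% to just under 70%)

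**3. Illustrative series.**

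| Series | Change from baseline | Change from smallest earlier scan | Rule A | Rule B |
|---|---|---|---|---|
| 100, 70, 48 | −30%, −52% | −30%, −31.4% | met | not met |
| 100, 70, 49, 34.3, 24.0 | −30%, −51%, −65.7%, −76% | −30% each time | met from second follow-up scan | never met |
| 100, 45, 45 | −55%, −55% | −55%, 0% | met and held | met, then not held |
| 100, 105, 48 | +5%, −52% | +5%, −52% | met | met |

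The third patient is flagged at once under both rules and can reach central review, but could be recorded locally as unconfirmed. The fourth is unaffected because the smallest earlier scan is still baseline.

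**4. One lost responder at a cut-off.** At stage 1, 2/24 becomes 1/24 and the trial stops. At the end, 5/35 (14.3%, exact 95% CI 4.8% to 30.3%) becomes 4/35 (11.4%, 3.2% to 26.7%) and the null is not rejected.

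**5. Trial-level sensitivity, by assumption only.** The documents give no share m of true responders missed. With a true rate of 20%, the observed rate is 0.20·(1 − m):

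- m = 5%: rate 0.19, power 0.816, early stopping 0.042
- m = 10%: rate 0.18, power 0.775, early stopping 0.054
- m = 20%: rate 0.16, power 0.673, early stopping 0.085

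With m = 0 these are 0.852 and 0.033.

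**The case against.** The best defence is that the protocol already settles the comparator. Section 8.1 says "The response will be determined as outlined in the RANO criteria below"; Section 4.1 says "Response will be assessed by RANO criteria"; Section 9.5.4 says "Efficacy will be determined by radiographic response and PFS using RANO criteria alone". PR (e) and (f) also refer to the baseline scan, and stable disease excludes a scan that qualifies for PR. Section 8.2 sets no threshold of its own. A full RANO read needs both comparisons, so comparing each scan with the smallest one can be understood as the progression check. Section 10.1 supports that guess: it refers to "a greater than 25% increase in the measurement of the tumor by MRI scan" without naming a reference scan. The harmful reading is also awkward, since it would make a held PR fail its own confirmation and leave percentage change undefined after a complete response.

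Most of this stands. The sentence was probably meant for progression, and many sites will read it so. First detection of a complete response is unaffected, and a gradual responder would still be flagged if a later scan halved the smallest one. No trial-level loss can be shown.

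The defence does not make the sentence correct. It says all scans, in the paragraph on confirming response, and followed literally it misclassifies gradual or held PRs. The other safeguards do not close the gap. The record review in 8.4 is optional and on a random sample, and source uploads (12.2) and remote monitoring (12.5) are not a systematic re-read of scans.

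**Conclusion.** The point holds: Section 8.2 is wrong as written. It conflicts with the PR definition in 8.1, and applied to the PR size criterion it misses any patient whose smallest earlier scan lies between 50% and 100% of baseline and whose new scan is at or below 50% of baseline but above half of that smallest scan.

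The conclusion is conditional on a site reading 8.2 that way, which the rest of the protocol discourages. The number of such patients, the share of sites and the loss of power cannot be derived from the documents; the power figures in step 5 only show how sensitive the design would be. The direction is certain: the error can lower the response rate and cannot raise the false positive rate. With decision limits that one patient can cross and no central read of unflagged patients, it should be fixed.

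**What to change.** Replace the sentence in Section 8.2 with wording to this effect: *For response and its confirmation, compare each scan with the baseline scan as in 8.1; for progression, compare with the smallest measurement to date as in 8.1.* State also that the regression percentage from central review is computed from baseline.

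Both comparators already stand in 8.1, so no new rule is introduced. The cost is one reworded sentence and one short clarification in an amendment. There are no added scans, visits or patients, and the sample size, decision rules and analysis do not change.
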